## **5.2. Dose Modifications**

The NCI Common Terminology Criteria for Adverse Events (CTCAE) Version 4.0 will be used to grade adverse events.

Subjects enrolled in this study will be evaluated clinically and with standard laboratory tests before and at regular intervals during their participation in this study as specified in Section 7. Subjects will be evaluated for adverse events (all grades), serious adverse events, and adverse events requiring study drug interruption or discontinuation at each study visit for the duration of their participation in the study.

A treatment-limiting adverse event is any adverse event related to study drug experienced during the study resulting in treatment termination.

### **5.2.1 Dose Modifications for Ginseng**

For subjects randomized to receive ginseng there are no dose delays or reductions. If regorafenib is held due to toxicity, the ginseng may continue if the toxicity is attributed to regorafenib only.

### **5.2.2 Dose Modifications for Regorafenib**

#### **5.2.2.1 Dose Reduction Levels**

The starting dose of regorafenib is 160 mg once daily. Study medication will be administered on a 3 weeks on/1 week off schedule [3 weeks out of every 4].

Doses will be delayed or reduced for clinically significant hematologic and non-hematologic toxicities that are related to protocol therapy according to the guidelines shown in the Dose Delays/Dose Modifications table that follows. Dose modifications will follow predefined dose levels. Dose adjustments for hematologic toxicity are based on the blood counts obtained in preparation for the day of treatment.

The modifications of regorafenib will follow the following predefined dose levels:		
Dose level 0 (standard starting dose)	160 mg orally every day	Four 40-mg tablets of regorafenib
Dose level - 1	120 mg orally every day	Three 40-mg tablets of regorafenib
Dose level - 2	80 mg orally every day	Two 40-mg tablets of regorafenib

If a subject experiences more than one toxicity, dose reduction should be according to the toxicity with the highest grade.

In the case of two or more toxicities of the same grade, the site investigator may dose reduce according to that deemed most causally related to study treatment.

If more than 2 dose reductions are required, regorafenib only will be discontinued and the rest of the study treatment may be continued. If a dose reduction has been performed, intra-subject dose re-escalation can be considered (up to the maximal 160 mg daily dose) at the discretion of the treating physician, provided that the toxicity(ies) has resolved to baseline.

The following tables outline dose adjustments for toxicities related to study drug except hand-foot skin reaction, hypertension, and liver function test abnormalities.

Recommended dose modification for toxicities except hand-foot-skin reaction, hypertension and ALT/AST/bilirubin			
NCI CTCAE v4.0 a	Dose Interruption	Dose Modification b	Dose for Subsequent Cycles
Grade 0-2	Treat on time	No change	No change
Grade 3	Delay until ≤ Grade 2 c	Reduce by 1 dose level	If toxicity remains < Grade 2, dose re-escalation can be considered at the discretion of the site investigator. If dose is re-escalated and toxicity (≥ Grade 3) recurs, institute permanent dose reduction.
Grade 4	Delay until ≤ Grade 2 c	Reduce by 1 dose level. Permanent discontinuation can be considered at site investigator's discretion.	

a. NCI-CTCAE = National Cancer Institute - Common Terminology Criteria for Adverse Events, version 4.0  
 b. Excludes alopecia, non-refractory nausea/vomiting, non-refractory hypersensitivity and nonclinical and asymptomatic laboratory abnormalities.  
 c. If no recovery after a 4 week delay\*, treatment should be permanently discontinued unless subject is deriving clinical benefit.

The table above outlines dose adjustments for hematologic and non-hematologic toxicities related to regorafenib except HFSR and hypertension.

In addition to these recommended dose modifications, subjects who develop diarrhea, mucositis, anorexia, or other events predisposing to fluid loss or inadequate fluid intake should be carefully monitored and rehydrated as clinically necessary. This is in order to minimize the risk of postural hypotension and renal failure.

Grading for Hand-Foot-Skin-Reaction			
	Grade 1	Grade 2	Grade 3
NCI-CTCAE v4.0 Palmar-plantar erythrodysesthesia syndrome a	Minimal skin changes or dermatitis (e.g., erythema, edema, or hyperkeratosis) without pain	Skin changes (e.g., peeling, blisters bleeding, edema, or hyperkeratosis) with pain	Severe skin changes (e.g., peeling, blisters, bleeding, edema, or hyperkeratosis) with pain
Further description / examples of skin changes	Numbness, dysesthesia / paresthesia tingling, painless swelling, or erythema of the hands and/or feet	Painful erythema and swelling of the hands and/or feet	Moist desquamation, ulceration, blistering, or severe pain of the hands and/or feet
Effect on activities	Does not disrupt normal activities	Limiting instrumental activities of daily life (e.g., preparing meals, shopping for groceries or clothes, using the telephone, managing money)	Limiting self-care activities of daily life (e.g., bathing, dressing and undressing, feeding self, using the toilet, taking medications) and not bedridden

a. Palmer-plantar erythrodysesthesia syndrome is a disorder characterized by redness, marked discomfort, swelling, and tingling in the palms of hands or the soles of the feet.

#### Recommended dose modification for hand-foot-skin reactiona

Grade of event	Occurrence	Suggested Dose Modification
----------------	------------	-----------------------------

(NCI-CTCAE v4.0)			
Grade 1	Any	Maintain dose level and immediately institute supportive measures for symptomatic relief	
Grade 2	1 st occurrence	Consider decreasing dose by one dose level and immediately institute supportive measures. If no improvement, interrupt therapy for a minimum of 7 days, until toxicity resolves to Grade 0-1 b, c	
	No improvement within 7 days or 2 nd occurrence	Interrupt therapy until toxicity resolves to Grade 0-1. c When resuming treatment, treat at reduced dose level b	
	3 rd occurrence	Interrupt therapy until toxicity resolves to Grade 0-1. c When resuming treatment, decrease dose by one dose level. b, d	
	4 th occurrence	Discontinue therapy	
Grade 3	1 st occurrence	Institute supportive measures immediately. Interrupt therapy for a minimum of 7 days until toxicity resolves to Grade 0-1. c When resuming treatment, decrease dose by one dose level. b, d	
	2 nd occurrence	Institute supportive measures immediately. Interrupt therapy for a minimum of 7 days until toxicity resolves to Grade 0-1. c When resuming treatment, decrease dose by one additional dose level b, d	
	3 rd occurrence	Discontinue treatment permanently.	

a. More conservative management is allowed if judged medically appropriate by the site investigator.
 
b. If toxicity returns to Grade 0-1 after dose reduction, dose re-escalation is permitted at the discretion of the site investigator if subject has completed one cycle at reduced dose without recurrence of event.
 
c. If there is no recovery after a 4-week delay, treatment with regorafenib will be discontinued permanently.
 
d. Subjects requiring > 2 dose reductions should go off protocol therapy.
 
e. The maximum daily dose is 160 mg.
			

The other study treatment may be continued.

**At first occurrence of HFSR, independent of grade, prompt institution of supportive measures such as topical emollients, low potency steroids, or urea-containing creams should be administered.**

Recommended prevention/management strategies for skin toxicities consistent with HFSR are summarized below:

### Control of calluses

Before initiating treatment with regorafenib:

- Check condition of hands and feet.
- Suggest a manicure/pedicure, when indicated.
- Recommend pumice stone use for callus or 'rough spot' removal.

During regorafenib treatment:

- Avoid pressure points.
- Avoid items that rub, pinch, or create friction.

### Use of creams

- Non-urea based creams may be applied liberally.
- Keratolytic creams (e.g. urea-based creams, salicylic acid 6%) may be used sparingly and only to affected (hyperkeratotic) areas.
- Alpha hydroxyl acids (AHA) based creams may be applied liberally 2 times a day. Approximately 5% to 8% provides gentle chemical exfoliation.
- Topical analgesics (e.g. lidocaine 2%) are to be considered for pain control.
- Topical corticosteroids like clobetasol 0.05% should be considered for subjects with Grade 2 or 3 HFSR. Avoid systemic steroids.

### Tender areas should be protected as follows:

- Use socks/gloves to cover moisturizing creams
- Wear well-padded footwear
- Use insole cushions or inserts (e.g. silicon, gel)
- Foot soaks with tepid water and Epsom salts

### Hypertension

Hypertension is a known AE associated with regorafenib treatment. Subject will have their blood pressure measured at every clinic visit or more frequently if clinically indicated. If additional blood pressure measurements are done outside the study site, and the blood pressure is > 140 mm Hg systolic or > 90 mm Hg diastolic (NCI CTCAE v4.0), then the subject must contact study personnel. The management of hypertension, including the choice of antihypertensive medication, will be performed according to local standards and to the usual practice of the site investigator. Every effort should be made to control blood pressure by medical means other than study drug dose modification. If necessary, the table below outlines suggested dose reductions.

Management of Treatment-Emergent Hypertension		
Grade (CTCAE v4.0)	Antihypertensive Therapy	Regorafenib Dosing
1  Prehypertension (systolic BP 120 - 139 mmHg or diastolic BP 80 - 89 mmHg)	None	
 
• Continue regorafenib
 
• Consider increasing blood pressure (BP) monitoring
 

2  Systolic BP 140 - 159 mmHg or diastolic BP 90 – 99 mmHg, OR Symptomatic increase by > 20 mmHg (diastolic) if previously within normal limits	
 
• Treat with the aim to achieve diastolic BP <math>\leq</math> 90 mm Hg:
 
• If BP previously within normal limits, start anti-hypertensive monotherapy
 
• If subject already on anti-hypertensive medication, titrate up the dose.
 
	
 
• Continue regorafenib
 
• If symptomatic, hold regorafenib until symptoms resolve AND diastolic BP <math>\leq</math> 90 mm Hga. When regorafenib is restarted, continue at the same dose level.
 


3
 
Systolic BP <math>\geq</math> 160 mmHg or diastolic BP <math>\geq</math> 100 mmHg OR More than one drug or more intensive therapy than previously used indicated
	
Treat with the aim to achieve diastolic BP <math>\leq</math> 90 mm Hg: Start anti-hypertensive medication
 
AND/OR Increase current anti-hypertensive medication
 
AND/OR Add additional anti-hypertensive medications.
	
 
• Hold regorafenib until diastolic BP <math>\leq</math> 90 mm Hg, and if symptomatic, until symptoms resolve.a
 
• When regorafenib is restarted, continue at the same dose level.
 
• If BP is not controlled with the addition of new or more intensive therapy, reduce by 1 dose level.b
 
• If Grade 3 hypertension recurs despite dose reduction and antihypertensive therapy, reduce another dose level.c
 

4
 
Life-threatening consequences (e.g., malignant hypertension, transient or permanent neurologic deficit, hypertensive crisis)
	
Per institutional guidelines
	
Discontinue therapy

a. Subjects requiring a delay of <math>>4</math> weeks should go off protocol therapy b. If BP remains controlled for at least one cycle, dose re-escalation permitted per site investigator's discretion. c. Subjects requiring <math>>2</math> dose reductions should go off protocol therapy.
		

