## **Side Effects**

May cause insomnia, nervousness, restlessness, increased heart rate, increased blood pressure or nausea.

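### For an already-treated, asymptomatic subject with diastolic pressure of 91–99 mmHg, the Grade 2 and Grade 3 rows of the hypertension table give opposite regorafenib instructions, and nothing says which governs

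*Combined protocol and SAP*

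**What the plan says.** The table in section 5.2.2 (Hypertension) ties a grade definition to an antihypertensive action and a regorafenib action.

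- **Grade 2.** The pressure limb reads "Systolic BP 140 - 159 mmHg or diastolic BP 90 – 99 mmHg, OR", followed by a symptomatic diastolic rise as the alternative. The antihypertensive column says "If subject already on anti-hypertensive medication, titrate up the dose". The regorafenib column says "Continue regorafenib", and then "If symptomatic, hold regorafenib until symptoms resolve AND diastolic BP" is 90 mmHg or lower, with restart at the same dose level.
- **Grade 3.** The pressure limb is systolic 160 or above, or diastolic 100 or above. A separate limb, joined by OR, is "More than one drug or more intensive therapy than previously used indicated". The antihypertensive actions include "Increase current anti-hypertensive medication". The regorafenib column says "Hold regorafenib until diastolic BP" is 90 mmHg or lower and any symptoms have resolved. Restart is at the same level, but dose reductions follow if pressure is not controlled or Grade 3 recurs. A footnote takes subjects who need more than two reductions off protocol therapy.

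The text above the table leaves management to local and investigator practice, asks sites to favour medical control of pressure over changes to study drug, and calls the dose reductions suggestions.

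Section 11 compares the arms on regorafenib pills taken out of 21 per cycle, on adherence defined as 17 or more of 21 days, on mean and median daily dose, and, by Fisher exact test, on toxicities, including the proportion with any toxicity of grade 3 or higher.

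**The concern.** Increasing an existing drug is the stated Grade 2 response. The need for more intensive therapy than before is, by itself, a Grade 3 definition. One act therefore places one event in two rows, and for some subjects those rows say opposite things about regorafenib.

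Two secondary analyses can be touched. A hold lowers the pill count and daily dose on which adherence is judged, and section 11 states no adjustment for holds that the protocol itself instructs. The row chosen also decides whether the event counts as grade 3 or higher.

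The controls receive no ginseng rather than a placebo, so sites make this choice knowing the arm. Section 9.1 (Side Effects) says of ginseng: "May cause insomnia, nervousness, restlessness, increased heart rate, increased blood pressure or nausea". The ambiguous situation could therefore arise more often in one arm, although the documents give no rate.

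**Working it through.** The plan states no figure on this point, so there is nothing to reproduce. The check applies both rows to each type of subject. Inputs are the two table rows, exclusion criterion 5 in section 3.2 (only uncontrolled hypertension is excluded, so treated and controlled subjects can enrol), and the precedence rule in section 5.2.2.1.

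| Subject whose pressure is in the Grade 2 range | Grade 2 row | Grade 3 row, through its therapy limb | Result |
|---|---|---|---|
| (a) Already treated, dose raised, asymptomatic, diastolic 91–99, systolic below 160 (e.g. 146/94) | Continue | Hold until diastolic is 90 or lower | Opposite instructions, two possible grades |
| (b) Already treated, dose raised, symptomatic | Hold until symptoms resolve and diastolic is 90 or lower | Same hold | Hold agrees; grade and later dose-reduction path differ |
| (c) Already treated, dose raised, asymptomatic, systolic 140–159, diastolic 90 or lower | Continue | Hold whose release condition is already met | Effectively agree; grade and later path differ |
| (d) Not previously treated, monotherapy started | Explicit Grade 2 action | No clear overlap | Outside this point |

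The direct contradiction is case (a). Cases (b) and (c) leave the grade open.

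Does any text break the tie? The rule in section 5.2.2.1 sends dose reduction to the highest grade when a subject has more than one toxicity. Case (a) is one toxicity that fits two rows. No other text separates a Grade 2 dose increase from Grade 3 intensification.

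Adherence, for illustration: a hold costing 5 dosing days gives 21 − 5 = 16, which is below 17, so the subject becomes non-adherent. A hold costing 4 days gives 21 − 4 = 17, still adherent. If a hold began at the nominal Cycle 1 Day 15 visit and were not reviewed until Cycle 2 Day 1, it would cost 7 dosing days (15 to 21), or 6 if the Day 15 dose had been taken, leaving 14 or 15. The length of such a hold is an assumption; the documents do not give one.

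**The case against.** The strongest reply is that the table is guidance. Sites manage hypertension by local practice, are asked to spare study drug where they can, and are offered the table as suggestions. This makes discretion part of the design, and the preference for medical control gives some direction in case (a). That much stands. It does not assign a grade, however, and it does not reconcile a row that continues the drug with a row that holds it.

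A second reply is that the highest grade should govern. The protocol does not say so for a single toxicity. If it did, the Grade 2 line for already-treated subjects could never operate with Grade 2 dosing.

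A third reply is that grades come from CTCAE v4.0, which the table heading and sections 5.2 and 10 name. Whether that source separates the two grades cannot be judged from these documents, so the grading ambiguity is claimed only as the protocol reads. Whichever grade it assigns, one of the two rows would still need editing.

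The limits on consequence also stand:

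- Exclusion criterion 5 bars diastolic above 90 despite optimal management, so a subject on optimal therapy must develop case (a) during the two 28-day cycles.
- In the comparison of grade 3 or higher toxicity of any kind, regrading changes a subject's status only if that subject has no other such event.
- Nothing shows that a hold for case (a) would last five dosing days.
- Both arms use the same table, and the ginseng section says only that raised blood pressure may occur.

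**Conclusion.** The inconsistency is real but narrow. It produces opposite regorafenib instructions for already-treated, asymptomatic subjects with diastolic 91–99 mmHg and systolic below 160 mmHg. For other already-treated subjects in the Grade 2 range whose dose is raised, only the grade and the later dose-reduction path are ambiguous. This rests on reading a dose increase as more intensive therapy, which the Grade 3 row supports by listing that same increase among its own actions.

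The number affected cannot be derived. It needs the share of subjects on an antihypertensive, the chance of reaching this pressure range, and the share who are then asymptomatic with diastolic above 90; the documents give none of these.

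Three stronger readings are tempting and are not supported:

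- **That every already-treated subject in the Grade 2 range receives opposite orders.** Cases (b) and (c) show otherwise.
- **That 18 to 45 subjects are in conflict.** Assuming that 20–50% of the 90 enter on an antihypertensive gives 0.2 × 90 = 18 to 0.5 × 90 = 45. That is an assumed pool at entry, not a count of those who reach case (a).
- **That the result is biased between arms, or that the fatigue endpoint is affected.** A difference between arms is possible but unquantified, and no effect on the primary endpoint is shown.

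The consequences are therefore confined to secondary analyses: pill counts, mean daily dose, and the grade 3 or higher comparison.

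**What to change.** Reconcile the Grade 2 and Grade 3 rows so that a subject whose existing antihypertensive is increased at 140–159/90–99 mmHg falls in one row, with one grade and one regorafenib instruction. The clinical team must decide which row governs; this review takes no position on it. Apply the resulting grade in the same way in both arms for the Fisher exact comparison in section 11. The cost is a wording change to one table at the next amendment, with no change to sample size or analysis method.

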### 3.2. Exclusion Criteria

1. Subject should not be receiving any agent for fatigue including steroids or megace.  
**NOTE:** Subjects who have a contrast-induced allergy are allowed to receive steroids for their scans.
2. Radiotherapy within 2 weeks prior to study registration. Subjects must have recovered from all therapy-related toxicities.
3. Prior treatment with regorafenib.
4. Previous assignment to treatment during this study. Subjects permanently withdrawn from study participation will not be allowed to re-enter study.
5. Congestive heart failure > New York Heart Association (NYHA) class 2.
  - Unstable angina (angina symptoms at rest), new-onset angina (begun within the last 3 months). Myocardial infarction less than 6 months before study registration.
  - Cardiac arrhythmias requiring anti-arrhythmic therapy (beta blockers or digoxin are permitted).
  - Uncontrolled hypertension (systolic blood pressure > 150 mmHg or diastolic pressure > 90 mmHg despite optimal medical management).
6. Evidence or history of bleeding diathesis or coagulopathy.
7. Any hemorrhage or bleeding event  $\geq$  NCI CTCAE Grade 3 within 4 weeks prior to study registration.
8. Subjects with thrombotic, embolic, venous, or arterial events, such as cerebrovascular accident (including transient ischemic attacks), deep vein thrombosis or pulmonary embolism within 6 months of study registration.
9. Previous or concurrent cancer that is distinct in primary site or histology from colorectal cancer within 3 years prior to randomization EXCEPT for curatively treated cervical cancer in situ, non-melanoma skin cancer and superficial bladder tumors [Ta (Non-invasive tumor), Tis (Carcinoma in situ) and T1 (Tumor invades lamina propria)].
10. Subjects with pheochromocytoma.
11. Known history of human immunodeficiency virus (HIV) infection or current chronic or active hepatitis B or C infection requiring treatment with antiviral therapy.
12. Ongoing infection > Grade 2 NCI-CTCAE v4.0.
13. Metastatic brain or meningeal tumors (symptomatic or asymptomatic).

14. Major surgical procedure or significant traumatic injury, as defined by the site investigator, within 28 days before study registration.
15. Renal failure requiring hemo- or peritoneal dialysis.
16. Dehydration Grade > 2 NCI CTCAE v4 within 7 days prior to registration.
17. Subjects with seizure disorder currently requiring medication.

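### Grade 3 hypertension row: for an asymptomatic subject with systolic pressure at or above 160 and diastolic at or below 90 mmHg, one reading meets both the hold and the restart condition for regorafenib

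*Combined protocol and SAP*

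**What the plan says.** The table is in protocol section 5.2.2, under Hypertension. Its Grade 3 row has three parts.

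- **Grade definition.** Systolic pressure of at least "160 mmHg or diastolic BP" of at least 100 mmHg. A further limb, the need for more than one drug or for more intensive therapy, is not a pressure reading and is left aside here.
- **Treatment aim.** "Treat with the aim to achieve diastolic BP" of 90 mmHg or less, by starting, increasing or adding antihypertensive drugs.
- **Regorafenib dosing.** "Hold regorafenib until diastolic BP" is at or below "90 mm Hg, and if symptomatic, until symptoms resolve". Then: "When regorafenib is restarted, continue at the same dose level". Further bullets call for a one-level reduction if pressure is not controlled on new or more intensive therapy, and another if Grade 3 recurs. Footnote a takes a subject off protocol therapy if a delay exceeds 4 weeks. The row gives no minimum length of hold.

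The text above the table leaves management of hypertension to local standards and the investigator's usual practice, and calls the table's dose reductions suggested.

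**The concern.** A hold should end when the condition that caused it has gone. Here the cause may be systolic or diastolic, but only diastolic pressure can end the hold. For isolated systolic hypertension without symptoms, the row therefore gives two opposite instructions at once: hold, because the subject is Grade 3, and resume, because diastolic pressure is already at or below 90 mmHg.

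Hypertension is described in the same section as a known adverse event of regorafenib, so what is at stake is a safety instruction that cannot be followed as written. Two sites faced with the same reading could act differently and both cite the protocol.

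**Working it through.** The plan states no figure to reproduce, and no sample size or power calculation is involved. The check is whether the readings that trigger a hold overlap with the readings that end it.

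**Grade 3, from the table.** SBP is systolic and DBP diastolic pressure, in mmHg.

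- Hold: SBP ≥ 160 or DBP ≥ 100.
- Restart: DBP ≤ 90 and no remaining symptoms.
- Both together: DBP ≤ 90 rules out the diastolic limb (DBP ≥ 100), so the hold must come from the systolic limb. The overlap is SBP ≥ 160, DBP ≤ 90, no symptoms. It is not empty.

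Illustrative readings, chosen here and not taken from the protocol:

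| Reading | Symptoms | Hold triggered by | Restart condition met at that reading? |
|---|---|---|---|
| 170/85 | no | systolic | yes |
| 170/85 | yes | systolic | no, until symptoms resolve |
| 170/95 | no | systolic | no, DBP is above 90 |
| 150/105 | no | diastolic | no, DBP is above 90 |

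Only the first line conflicts. That subject is still Grade 3 by the row's own definition at the moment restart is allowed. The overlap has no upper systolic bound within Grade 3, because Grade 4 is defined by life-threatening consequences and not by a pressure value.

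**Grade 2, from the same table.** Without symptoms, the drug continues. Only symptoms trigger a hold: "If symptomatic, hold regorafenib until symptoms resolve AND diastolic BP" is at or below 90 mmHg.

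- Hold: Grade 2 with symptoms.
- Restart: symptoms resolved and DBP ≤ 90.
- Both together: impossible, since one needs symptoms and the other their absence. A subject at 150/85 whose symptoms resolve is an asymptomatic Grade 2 subject, for whom the row continues the drug anyway.

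**Does another rule settle the Grade 3 case?**

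- The general toxicity table in section 5.2.2.1 delays a Grade 3 event until it falls to Grade 2 or lower, but the text introducing it excludes hypertension.
- The other restart rules follow their own trigger: general toxicities by grade, hand-foot-skin reaction by return to Grade 0-1, transaminases by the transaminases themselves. The hand-foot-skin table also sets a 7-day minimum for a Grade 3 event. The hypertension row has no such floor, and its 4-week footnote is a ceiling.
- The bullet on uncontrolled pressure concerns dose reduction. It does not define control and leaves the restart condition as it is.

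**The case against.** The strongest reply is that the table is not the whole of management. Local standards govern, the reductions are suggested, the row directs antihypertensive treatment, and the bullet on uncontrolled pressure refers to blood pressure in general, so persistent systolic elevation could be caught there. A subject still at 160 systolic is also still Grade 3, so the hold applies on its face. Section 6.2 lets the investigator stop treatment on judgment. All of this stands as mitigation. It means the row is ambiguous between hold and restart and does not positively order a hold of zero length. It does not remove the ambiguity: the only pressure target written down is diastolic, and control is undefined.

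A reader might also infer more than the documents support:

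- **That every subject held for systolic pressure may restart at once.** Untrue when diastolic is above 90 or symptoms are present.
- **That the Grade 2 row has the same fault.** It does not, as shown above.
- **That the row contradicts eligibility.** Section 3.2 excludes "systolic blood pressure > 150 mmHg or diastolic pressure > 90 mmHg despite optimal medical management". That limit concerns entry to the trial, and a restart rule for an on-treatment toxicity need not match it. It shows only that the protocol elsewhere gives systolic pressure a limit of its own.
- **That the arm comparison is biased.** Section 9.1 says ginseng may cause "increased heart rate, increased blood pressure or nausea", but gives no rate, and the table is the same in both arms. An effect on the toxicity, adherence or fatigue comparisons is possible, but nothing in the documents shows it. Section 11 does not say how held days count towards adherence.

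**Conclusion.** The Grade 3 row contradicts itself for one defined group: asymptomatic subjects with systolic pressure at or above 160 and diastolic at or below 90 mmHg. For them the hold and the restart conditions are met by the same reading, with restart at the same dose level.

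The documents do not say how many of the planned 90 subjects might be affected, so the size is a definable set of readings and not a rate. There is no direct consequence for sample size or power. The conclusion assumes that the restart condition may be judged on the reading that triggered the hold, since the row sets no minimum interval. It rates as minor safety wording that is wrong as written.

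**What to change.** The sponsor should reconcile the restart condition and the treatment aim in the Grade 3 row with that row's systolic-or-diastolic definition of the grade, so that a subject held on systolic pressure has a restart condition that bears on the reason for the hold. Whether that needs a pressure value, and which one, is for the clinical team; none is proposed here.

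The cost is wording in one table row, made by an amendment under section 13.4. No extra measurement is needed, because blood pressure is already taken at every clinic visit. The Grade 2 row and the eligibility criterion need no change on this account.
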